
MILESTONE 1. Completion of Alpha [REDACTED] Review within 30 days.

B.1.2. Beta Version Development. Beta Version Development for this project will be orchestrated by the Oui development team (including four team members identified as Other Personnel in the Budget Justification) who operate in 30-day development cycles (also called sprints). The Oui development team is a collection of individuals working together to deliver the requested and committed product increments (or iterations). Within the sprint, our development team (see Other Personnel in Budget Justification) will build the Beta [REDACTED]

MILESTONE 2. Completion of Beta [REDACTED] within 30 days.

B.2. Specific Aim 2 – To test the feasibility and acceptability of the beta version of [REDACTED] in a single-group, open-label trial.

B.2.1. Primary Objective. The primary objective of the feasibility portion of the project is to assess the feasibility, and usability of [REDACTED] to deliver targeted CBT to adolescent patients recently hospitalized for SI or suicide attempts. The secondary objectives of this study are to assess the effects on SI and behavior in a

pre/post design of [REDACTED] with adolescent patients being discharged from a hospital.

B.2.2. Endpoints. Consistent with the primary objectives of assessing feasibility, and usability of the intervention, the primary endpoints of this study will be to measure rates and descriptions of recruitment, attrition, data collection, study resources, intervention delivery and acceptability. Hence, our data for this Aim will be descriptive in nature. Formal statistical comparisons will not be performed. Our study will hence focus on process, consistent with a feasibility study. Semi-structured interviews will be conducted by a mental health professional with patients via telephone (according to the Timeline in the Human Subjects and Clinical Trials Information section). Interviews will be recorded digitally for internal use by ADC staff only (e.g., rater training and interrater reliability reviews) and will not be shared with Oui, Therapeutics. Study data will be entered into REDCap. We will use the System Usability Scale (SUS), the Utility of Techniques (UT) questionnaire and also conduct a semi- structured user feedback interview to systematically capture usability and accessibility.

B.2.3. Usability and Acceptability. The SUS is a valid and reliable, 10-item measure that can be used to effectively differentiate between usable and unusable systems among adolescents and adults (Dexheimer, et al., 2017; Brooke, 1996). Sample items are "I think that I would like to use this app frequently" and "I felt very confident using the system." Responses are rated using a 5-point (strongly disagree to strongly agree) Likert scale. Scores range from 0 to 100. A score of 68 is the minimal indicator of usability.

B.2.4. User Feedback Interview Questions. Participants and parent/guardians will be asked to give their feedback about experiences using the app and any suggestions for improving the app. The Utility of Techniques (UT) questionnaire will determine perceived helpfulness of the strategies taught in [REDACTED]. The questionnaire will ask about each component of [REDACTED] separately. For each [REDACTED] session, participants will be asked: Did you use the skills presented in this session? Which ones? Were they helpful?

B.2.5. Secondary Endpoints. Diagnostic interviews will be conducted with each participant with the **Mini International Neuropsychiatric Interview Neurocognitive for Children and Adolescents (MINI-KID)**, a widely used, structured diagnostic interview that will be used to verify diagnosis at the screening visit (Sheehan et al 2010). Secondary endpoints will consist of the following measures, assessed using a within-group comparison, over time: **1) Suicidal ideation.** The Suicide Ideation Questionnaire (SIQ) is a 30 – item self or clinician administered instrument used to measure the current intensity of patients' specific distress and suicidal intent, which has been validated for use with adolescents (Pinto et al 1997). Score range is 0-180, with higher score indicating higher intensity. **2) Suicide attempts and other behaviors.** This outcome will be assessed via the Columbia Suicide Severity Rating Scale (CSSRS), which was designed to classify suicide attempts, aborted suicide attempts, and other suicidal behaviors and has been validated for use with adolescents (Gipson et al 2015). **3) Depressive symptoms.** The Patient Health Questionnaire (PHQ-9) is a 9-item self-report form to assess the severity of depressive symptoms that has been widely used in practice and research and validated for use with adolescents. This will be used throughout the study to assess severity of any depressive symptoms each subject is experiencing (Richardson et al 2010).

B.2.6. Participant Remuneration for follow-up sessions. All participants will be paid \$20 for completing each post-discharge assessment (weeks 1, 4, 8, 12, and 16; \$100 total) and a \$25 bonus for completing all assessments. Adolescents and parents/guardians will be paid separately, with separate ClinCards, for their participation (maximum \$125 each). Data from parent/guardians will continue to be collected in cases where participants reach age of maturity during study participation so long as the child continues participation in the study as an adult (i.e., signs adult informed consent form). Parent/guardian date of birth is required in order to register the ClinCards to the parent/guardian. This information will be collected during the consenting process. Payments will not be prorated for partial completion of assessments. Sufficient funding has been budgeted for this portion of the project (see Budget Justification).

B.2.7. Inclusion Criteria. Qualified subjects will meet all of the following criteria:

Patients of any gender, age 13-17 years
Inpatient psychiatric patients who have attempted suicide (lifetime) or have documented SI and a plan to harm themselves at admission
Understand written and spoken English
Own an iPhone with iOS 11 or higher, or Android with OS 8.1 or higher
Willing and able to complete enrollment procedures
Parent/guardian (and youth) able to understand the nature of the study and provide written informed consent (assent for youth)
Willing to agree to release of information to their parent/guardian and providers when clinically indicated.

B.2.8. Exclusion Criteria. Subjects who meet any of the following criteria are disqualified from this study:

Patients with active psychosis
Patients experiencing substance withdrawal

Currently enrolled in other treatment studies for the symptoms and behaviors targeted
Patient unwilling or unable to wear mask during in-person study procedures
Patients who, in the judgment of the investigator, would have an unfavorable risk/benefit profile with respect to [REDACTED]
Any other psychiatric or medical condition (e.g., intellectual disability) or custody arrangement that in the investigator's opinion would preclude informed consent/assent or participation in the trial.

B.2.9. Safety Evaluations. Adverse events (AEs) will be assessed at each study visit and will be reported according to Policy 910. AEs will be assessed with the questions "Have there been any changes to your physical health since the last study visit (or "start of the visit" if it is the first study visit)" and "Have there been any changes to your mental health since the last study visit (or "start of the visit" if it is the first study visit)". Assessments will be carried out throughout the study to help participants in need of more extensive support know when to contact their usual care provider and be guided to crisis contact services.

MILESTONE 3. Completion of the feasibility study within 6 months.

B.2.10. Data Processing and Analysis Plan. Data processing and analyses will be completed within 60 days and will be primarily descriptive. Data analyses will address the outcomes relating to the feasibility of [REDACTED] and study procedures. Data collected will be used to determine whether revisions should be considered before proceeding to a controlled trial.

MILESTONE 4. Completion of Data Processing and Data Analysis within 2 months.

B.2.11. Rationale for Number of Subjects. We will recruit 20 youth age 13-17 years who complete enrollment in the [REDACTED] app. Expecting 10% attrition rate before completing enrollment in the [REDACTED] app we will consent 22 youths to reach our target enrollment number of 20. Means, medians, ranges, and standard deviations for the length of time taken for patients to work through the intervention and for patients to complete the eligibility interview, baseline, post-treatment (8 weeks) and follow-up (12 and 16 weeks) assessments will be reported. In addition, means and SDs will be reported for the length of time it takes project personnel to administer the data collection procedures from invitation through treatment. These data will be used to assess the feasibility of the intervention and study procedures. They will also be used for formal power calculations to design an adequately powered RCT in a subsequent project.

TIMELINE

	Screening Period ^{a, f}	App Testing Period					Follow-Up Period	
Week(W)	W0	W1 ^b	W1-3	W4 ^b	W5-7	W8 ^b	W12 ^b	W16 ^b
Informed Consent	X							
Participant Information Sheet ^c	X							
Medications at Discharge (from medical record)	X							
Medication history form (parent report)		X		X			X	X
Research team phone call with outpatient provider		X						
Enrollment in [REDACTED]	X							
Mini-international neuropsychiatric interview (MINI-KID)	X							

Health Screen Interview	X							
Suicide Ideation Questionnaire (SIQ)	X	X		X		X	X	X
AE Assessment)	X	X		X		X	X	X
Patient Health Questionnaire (PHQ-9)	X	X		X		X	X	X
Columbia Suicide Severity Rating Scale (C-SSRS) - lifetime	X							
Columbia Suicide Severity Rating Scale (C-SSRS) – since last contact		X		X		X	X	X
Frequency of Use of App ^d		X	X	X	X	X	X	X
Interviews for feedback [REDACTED]		X		X		X	X	X
Utility of Techniques		X		X		X	X	X
Usability and Acceptability ^e		X		X		X	X	X
Assessment of healthcare resource utilization (parent report)		X		X		X	X	X

a Screening will be conducted while adolescent patients are at an inpatient psychiatric facility.

b Over the phone with member of the research team

c Sheet to collect demographic and contact information

d Unique logins and duration of each login

e System Usability Scale

f Visit 0 may take place over multiple sessions

RECRUITMENT AND RETENTION PLAN

Enrollment Procedures. Eligible participants will be identified through medical record review. Consultations will be completed with participant's attending psychiatrists to confirm eligibility. Attending psychiatrists will be asked to inform the parent and patient that they will be contacted by staff about a research study; however, only IRB-approved study staff (without a treatment relationship with the patient) will recruit participants. When possible, parents and participants will be invited to participate in the study together. However, given that participants are inpatients and housed separately from parents, in most cases parents and patients will be invited to participate separately. When parents are not on site, IRB staff will call parents to invite them to participate. If parents agree, a remote consenting procedure will occur. Patients will all provide assent in person. Behavioral observations will be used as an additional indicator of assent. If patient's behavior does not indicate assent (e.g., avoiding eye contact, withdrawn) the participant will not be enrolled. Participants will not be recruited on the patient's first day of admission.

Retention Methods. We recognize that obtaining follow-up data is critical. Therefore, we will take several steps to optimize our ability to collect such data. During the informed consent process, participants (parents/guardians) will be asked to provide multiple forms of contact including a direct telephone contact and e-mail as well as the back-up numbers of at least two family members or friends in case study staff are unable to reach the participant at the direct number. If study staff is unable to reach the participant for follow-up at all contact numbers provided following no less than three call attempts, then a letter will be sent to the participant requesting that they contact the study staff. If no reply is received from 1 week of mailing the first letter, then a second letter will be sent requesting that the participant contact the study staff and also indicating a date by which study staff will no longer contact them to schedule follow-up calls. If no reply is received by the indicated date, then the participant will be considered lost to follow-up and will be withdrawn from the study.

Early Withdrawal of Participants. Participants may voluntarily withdraw from the feasibility study at any time. They may contact the site PI at the phone number(s) listed on the informed consent document. Participants may be withdrawn from the feasibility study by the site PI if they no longer meet eligibility criteria, are unable to be contacted (lost to follow-up) or are otherwise unable to complete study procedures, or are determined to be adversely affected by content in [REDACTED]. Participants who attempt suicide while an active participant in the study will continue to be enrolled in the study so long as no criterion for withdrawal (e.g., no longer meet study criteria, adversely affect by content in [REDACTED]) is met. Participants will have access to the app for the duration of their participation in the study. Participants who withdraw or are withdrawn early from the feasibility study will no longer have access to the app.

PROTECTION OF HUMAN SUBJECTS

RISKS TO HUMAN SUBJECTS.

Human Subjects Involvement, Characteristics, and Design. The Institute of Living (IOL) leadership has consented to permit recruitment of patients to volunteer to participate in the feasibility study (see e-mail from [name], Medical Director). The proposed feasibility study will include 22 (of which 20 are expected to complete enrollment in the [REDACTED] app) adolescent patients from the IOL's CARES and Adolescent Psychiatry Units at Hartford HealthCare, who have attempted suicide (lifetime) or have clinically significant suicidal ideation and a plan to harm themselves.

Study Procedures, Materials, and Potential Risks. All participants will receive access to the Beta Version of [REDACTED] for the feasibility study. There are risks of emotional discomfort and distress from talking about suicide and other sensitive topics. There is also the risk that confidentiality may be broken.

ADEQUACY OF PROTECTIONS AGAINST RISKS.

Informed Consent. Using procedures approved by Hartford HealthCare's IRB, participants' parent/guardian will be able to provide informed consent and participants will provide assent. IRB-approved study staff will inform potential participants about the voluntary nature of their participation and that their data will remain confidential. We will inform participants that we have an NIH certificate of confidentiality. We will communicate the limits of confidentiality, which include reports of imminent suicide risk, homicide risk, abuse of vulnerable individuals (e.g., minors, elderly, and individuals with intellectual disability), and compliance with federal, state or local laws. In these instances, we will report to the appropriate authorities and/or provide participants with referrals for immediate treatment. Patients will also be informed that they have the right to not participate, or to stop participating in the feasibility study at any time.

Protections Against Risk. Participants will be given an identification number, which will be matched to participant names in a password-protected electronic document, which will only be accessible to IRB-approved study staff. Participant data will be entered into REDCap or stored on HHC's HIPAA compliant servers. Only

coded data will be shared with Oui through REDCap or other secure data transfer system. We recognize that our population will include patients who may have arrived to the hospital in crisis, and our procedures have the potential to cause emotional distress. For these reasons, participants will not be recruited for the study on the first day of admission.

Potential Benefits of the Proposed Research to Research Participants and Others. The benefits of crisis response planning and follow-up after a hospital visit for suicidal ideation have been well-documented in the research of Drs. [name] and [name]. A digital approach will provide these resources and evidence-based support systems to individuals who otherwise might go without them.

Importance of the Knowledge to be Gained. The proposed research offers a way to expand access to crisis response planning and aftercare for adolescent patients at high risk of suicide. A mobile technology approach to this type of intervention would allow adolescent patients to access care faster, less expensively, and more reliably than they do today.

Risk Management. Suicidal ideation/behaviors will be assessed during each study interview (Week 0, Week 1, Week 4, Week 8, Week 16). Week 0 is the study baseline assessment, which occurs while the participant is housed in an inpatient treatment facility. For purposes of risk management, results of the study assessment at Week 0 will be shared with the inpatient treatment team in order to provide information relevant to their treatment/discharge planning. Remaining assessments are conducted by phone. In order to facilitate risk management during these calls we will do the following: 1) only enroll participants who provide assent/consent for the study to release information to their parent/guardian (note a parent/guardian interview is also routinely completed at this time), 2) only enroll participants who provide assent/consent for the study to release information to their outpatient provider (note that provider information may not be known at the time of consent in which case authorization will be obtained at the earliest possible time after provider information is known prior to making the initial outpatient provider call), 3) obtain location information at the start of each phone assessment, and 4) schedule phone assessments at a time when the parent/guardian is present at the same location as the participant. In addition to the routine outpatient provider call at week 1, increases in suicide risk will be communicated to the parent/guardian and outpatient provider. Details of study assessments indicating changes (i.e., increases) in risk since the previous assessment will be shared with the parent/guardian and outpatient provider. In addition, interviewers will engage in risk management interventions as clinically indicated following the guidelines outlined in the Risk Management Documentation Form. For patients scoring in the moderate or high-risk categories, a follow-up contact will be made with the parent/guardian and/or outpatient provider within 48 hours of the study call to assess follow-through with risk management recommendations provided by the study clinician. Participants will be informed that information they input to the app is not monitored for purposes of risk assessment.

AE Reporting. Adverse events (AEs) will be monitored and documented at each study visit. Reporting of AEs will follow the Hartford HealthCare Institutional Review Board Policy 910 and NIMH policy. Given that all enrolled participants will have a history of suicidal ideation with plan, AEs related to suicidal thoughts/behaviors, including death by suicide, will be categorized as "expected". Further, AEs meeting any of the following criteria will be categorized as "Serious": results in death; is life-threatening (places the subject at immediate risk of death from the event as it occurred); requires inpatient hospitalization or prolongation of existing hospitalization; results in a persistent or significant disability/incapacity; results in a congenital anomaly/birth defect; an important medical event, based upon appropriate medical judgment, may jeopardize the subject's health and may require medical or surgical intervention to prevent one of the other outcomes listed in this definition; or results in a severely debilitating situation for the subject, such as psychological distress, financial hardship or damaging impact on social standing or employability. AEs which are unexpected, related, and serious will be reported to the HHC IRB within 7 calendar days and to the NIMH PO within 10 business days. Death related to the study will be reported to the NIMH PO within 5 business days. All other AEs will be documented and reported to HHC IRB and NIMH PO at the time of the respective annual progress reports.

OUI's DATA SECURITY AND RESOURCE SHARING PLAN

The PI, [name], and the Research Coordinator, [name], both have extensive experience in digital health and privacy protection through previous projects at Cobalt and Magellan Health where they developed and implemented eight patient facing apps (now accessible in the Google Play and Apple App Store), and other digital health products that required data protection for more than 50 million covered lives. They have undergone annual HIPAA compliance trainings over the last five years and have overseen the data compartmentalization for tens of thousands of users. They both have more than a decade of experience delivering programs with personalized user experience in safe, secure environments designed to mitigate risk. As Research Coordinator, [name] will serve as the Privacy and Security Officer and his responsibilities will include ensuring that: (1) Oui and affiliated partners are adequately trained and are following HIPAA guidelines; (2) Oui HIPAA Compliant servers are generating de-identified datasets to offer increased protection for patient privacy through masking of direct and some indirect identifiers; and (3) appropriate levels of security will be used for transferring data or providing access with a secure system to provide additional safeguards.

The dataset available for resource sharing by Oui will not have personal identifiers. Before data will be shared to prospective users, they must agree to the conditions of use governing access to the public release data, including restrictions against attempting to identify study participants, destruction of the data after analyses are completed, reporting responsibilities, restrictions on redistribution of the data to third parties, and proper acknowledgement of the data resource. The information provided by users (i.e. feedback session participants) will not be used for commercial purposes. During their participation in feedback sessions, participants will download and use [REDACTED]. Data collected through [REDACTED] may be shared with the app development team according to its Terms of Service with users. These data will be used internally to conduct data analytics aimed at improving [REDACTED] and customizing user experience, and their disclosure would compromise Oui's intellectual property and competitive advantage. All data supporting published scientific results will be de-identified and added to the shared data products described above.

Cybersecurity and Data Collection. The team at Oui has developed and implemented certain measures to ensure cybersecurity and data protection on previous digital platforms. [REDACTED] is built on the fundamental principle of anonymity with security and privacy engineered into the core design. This includes (1) applying a security framework, and (2) ensuring data segregation of Protected Health Information (PHI). The data will not retain participant names when entered into our system and will only be accessible by authorized users. Our measures to ensure cybersecurity and data protection include:

1. Unique password-protected user accounts.
2. Strong password requirements. User passwords will be required to be 8 or more characters in length.
3. Security and penetration testing.
 - a. Security culture. The technology group's primary tool to ensure security for the users will be by starting with a security culture. All server-side processes run in docker containers with minimal privileges. Access to non-development environments will be restricted to few employees and policy requires it to be used only in emergency measures and with oversight.
 - b. Communication. Connectivity to and within [REDACTED] will be severely restricted, and all communication will be encrypted.
 - c. Role-based production access. Access across all deployment tiers (development, beta, production) leverages a role-based entitlement system that associates privileges with a certain role, which will be then associated with appropriate users to ensure comprehensive access management.
 - d. Data encryption. All data will be decrypted only in-memory and encryption keys provide a second check on access controls.
 - e. Auditing. All activity within, access of, and attempted access of [REDACTED] will be monitored, logged, and stored for anomaly detection and auditing.

f. Testing. A [REDACTED] will be declaratively provisioned and will have an extensive testing process run with automated scripts.

REFERENCES

Asarnow, J. R., & Mehlum, L. (2019). Practitioner Review: Treatment for suicidal and self-harming adolescents—advances in suicide prevention care. *Journal of child psychology and psychiatry*, 60(10), 1046-1054.

Beck, A. T. (1979). *Cognitive therapy and the emotional disorders*. Penguin.

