6.1.2 COLUMBIA-SUICIDE SEVERITY RATING SCALE (C-SSRS)

The C-SSRS is a rater-based interview to assess the severity and intensity of suicidal ideation and behaviors. Results will be presented for each question and within each of four constructs using counts and percentages over time: at week 4, week 8, and week 12.

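### The protocol's pre/post assessment of suicidal behaviour has no comparable baseline (lifetime C-SSRS at W0, windows of 1 to 4 weeks afterwards), and the SAP supplies no analysis in its place

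*Protocol*

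**What the plan says.** Protocol B.2.1: "The secondary objectives of this study are to assess the effects on SI and behavior in a" pre/post design. Protocol B.2.5 then lists suicidal ideation (SIQ), suicide attempts and other behaviours (C-SSRS) and depressive symptoms (PHQ-9), introduced by: "Secondary endpoints will consist of the following measures, assessed using a within-group comparison, over time".

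The protocol Timeline has two C-SSRS rows. "Columbia Suicide Severity Rating Scale (C-SSRS) - lifetime" is marked at W0 only. "Columbia Suicide Severity Rating Scale (C-SSRS) – since last contact" is marked at W1, W4, W8, W12 and W16. No C-SSRS with a recent look-back is scheduled at W0. The SIQ and PHQ-9 are each a single row marked at W0 and at every follow-up call.

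SAP 6.1.2 presents the C-SSRS as "counts and percentages over time: at week 4, week 8, and week 12". It lists no baseline, W1 or W16 column. SAP 1.1.1 judges potential for effectiveness from pre-test and post-test scores for ideation and depression, and does not name behaviour. Its assessment list runs from baseline to week 12, with no week 16.

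Protocol B.2.2 says that no formal statistical comparisons will be made.

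**The concern.** A pre/post contrast needs the same quantity on both sides. Here the only scheduled C-SSRS value before the app asks whether a behaviour ever happened. Each value afterwards asks whether it happened in the last few weeks. Lifetime status cannot fall, and B.2.7 selects patients with a lifetime attempt, or ideation with a plan at admission, so the baseline will be high by design. A short window will look better whether or not the app does anything. The SIQ and PHQ-9 do not fill the gap, because as B.2.5 describes them they measure ideation and depressive symptoms, not attempts.

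The study is meant to inform a controlled trial (B.2.10), and the Innovation section says that the next line of research would take suicide attempts as the primary outcome. A misread behaviour result, or an incomplete count of on-study events, would carry into that planning.

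**Working it through.** **Plan's own figure.** Neither document gives an expected rate or change for this endpoint, so there is nothing to reproduce. The only planned number used is the 20 participants.

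**Windows.** Visit weeks are 0, 1, 4, 8, 12 and 16 (Timeline). Successive differences give 1, 3, 4, 4 and 4 weeks. The protocol's Risk Management paragraph lists suicidality assessments at weeks 0, 1, 4, 8 and 16, without week 12. Read that way, the last window would be 8 weeks, so it needs reconciling with the Timeline.

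**W0 against follow-up, no app effect.** Let L be the share with a lifetime attempt and T the years at risk before entry. Both are assumptions: L = 30 to 90%, T = 1 to 5 years. With a constant rate:

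- rate per year: λ = −ln(1 − L)/T
- expected share with an attempt in w weeks: 1 − exp(−λw/52)

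Example, L = 50% and T = 3: λ = 0.693/3 = 0.231. For w = 4 the share is 1 − exp(−0.231 × 4/52) = 1.8%. That is 0.35 of 20 participants against 10 of 20 at W0, an apparent fall of 48.2 points.

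| L | T (years) | 4-week share | Apparent fall (points) | 16-week share | Apparent fall (points) |
|---|---|---|---|---|---|
| 30% | 1 | 2.7% | 27.3 | 10.4% | 19.6 |
| 30% | 5 | 0.5% | 29.5 | 2.2% | 27.8 |
| 50% | 1 | 5.2% | 44.8 | 19.2% | 30.8 |
| 50% | 3 | 1.8% | 48.2 | 6.9% | 43.1 |
| 50% | 5 | 1.1% | 48.9 | 4.2% | 45.8 |
| 90% | 1 | 16.2% | 73.8 | 50.8% | 39.2 |
| 90% | 5 | 3.5% | 86.5 | 13.2% | 76.8 |

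The fall to a 4-week window is 27 to 87 points. Pooling all 16 weeks still leaves about 20 to 77.

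**Could a higher rate after discharge cancel it?** For a 4-week share to equal L, the rate would have to rise by a factor of 52T/4 = 13T: 13-fold at T = 1 and 65-fold at T = 5.

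**Matched windows.** With 16 weeks before and 16 weeks after, the same model at L = 50%, T = 3 gives 6.9% on each side, an expected difference of 0.

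**Unequal windows within follow-up.** At an assumed 2% weekly hazard, W4 (3 weeks) gives 1 − 0.98³ = 5.9% and W8 (4 weeks) gives 1 − 0.98⁴ = 7.8%. The difference is 1.9 points, or 20 × 0.019 = 0.4 of one participant. W8 and W12 have equal windows. A participant who missed W4 would have a 7-week window at W8, 1 − 0.98⁷ = 13.2%.

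**What the SAP table omits.** Because the form asks about the time since the last contact, a behaviour reported at W1 is not asked about again at W4, and one first reported at W16 comes after the last column. Of the 16 weeks, columns at W4, W8 and W12 cover 3 + 4 + 4 = 11. They miss the first week and the last four.

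**The case against.** The strongest reply is that the SAP has already narrowed the protocol. It plans no lifetime contrast, keeps pre/post for ideation and depression, and tabulates the C-SSRS during follow-up only, which is close to on-study incidence. Nothing is tested, and no decision rule uses behaviour. Suicidal behaviours are also handled as adverse events, and SAP 5.1 and 5.2 count both participants and events.

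Much of this stands. A reader might infer that the planned report will show a spurious fall; SAP 6.1.2 as written would not print one. A reader might also infer a false significant result; B.2.2 rules out formal comparisons. But the protocol still states behaviour as a pre/post objective, and the SAP leaves that objective with no analysis rather than a valid one. The adverse event tables do not close the gap. They rest on general questions about changes in physical and mental health (B.2.9) and are grouped by MedDRA term, not by the C-SSRS classes of behaviour.

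Two further inferences go too far. One is a fall of 93 to 98 points, which needs every participant to have a lifetime attempt; B.2.7 also admits ideation with a plan and no attempt. The other is a materially distorted trend within follow-up. At 20 participants the W4 to W8 difference is a fraction of one person, and the 2% hazard behind it, which implies 1 − 0.98¹⁶ = about 28% with an event over 16 weeks, has no source in the documents.

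Finally, the W0 case report form is not in the documents and may already record dates. That affects the cost of one fix, not the point.

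**Conclusion.** The point holds for the C-SSRS behaviour endpoint only. The mismatch of look-back periods is plain from the Timeline. The direction of the artefact held across the whole assumed range. Its size, 27 to 87 points for a 4-week window, is illustrative and rests on a constant rate and on assumed values of L and T.

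In practice, the protocol's behaviour objective has no valid analysis: the only scheduled C-SSRS baseline cannot serve, and the SAP offers no substitute. Separately, the SAP table leaves out behaviour first reported at W1 or W16. The first of these falls within the month after discharge that the protocol's own background singles out as high risk. Because the study is descriptive, the consequence is a misleading or incomplete summary of a secondary endpoint. The matter should be corrected but does not threaten the feasibility aims.

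**What to change.** 1. **Protocol B.2.1 and B.2.5.** State that suicidal behaviour is reported as on-study incidence and is not compared with the lifetime C-SSRS. If a pre/post contrast is wanted, and the W0 form does not already record dates, record the date of each behaviour at W0 and compare the 16 weeks before admission with the 16 weeks after. State that the earlier window contains the index crisis, so regression to the mean remains even with equal windows.
2. **SAP 6.1.2.** Add the cumulative number of participants with each behaviour over all calls, W1 to W16, with the actual follow-up time covered. Align the SAP 1.1.1 assessment list and the protocol's Risk Management list with the Timeline for weeks 12 and 16. Person-week rates are optional at this sample size.

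Cost: wording changes, one extra summary and, at most, one or two date fields in an interview already scheduled. The downside is a behaviour result that looks less favourable than a comparison with lifetime history would.
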